2.3 Study objectives

The primary objectives of this study are:

- to determine the tolerability, adverse event profile, maximum tolerated dose (MTD), and dose-limiting toxicities (DLTs) of NOX66 in a suppository dosage form in patients with refractory solid tumours, both as a single agent and in combination with carboplatin
- to determine if NOX66 in a suppository dosage form is able to combine with a standard dosage of carboplatin to produce a meaningful anti-cancer effect in solid tumours considered to be refractory to cytotoxic chemotherapy
- to determine if NOX66 in a suppository dosage form (NOX66) is able to combine with a dosage of carboplatin two-thirds of the standard dosage to produce a meaningful anti-cancer effect in solid tumours considered to be refractory to cytotoxic chemotherapy.

The secondary objectives are:

- to characterise some key pharmacokinetic features of NOX66 when administered rectally
- to determine if various biomarkers of NOX66 biologic activity have any correlation to the efficacy or toxicity of NOX66 in combination with carboplatin.

3. ANALYSIS POPULATIONS AND GENERAL STATISTICAL METHODOLOGY

This analysis plan is based on protocol version 3.0, dated 30 June 2017.

3.1 Analysis populations

There will be three study populations defined for this study.

The safety population will consist of all patients who received at least one dose of NOX66. This population will be used in all safety summaries.

The efficacy population will consist of all patients with measurable or evaluable disease at baseline who complete at least 1 cycle of combination treatment and undergo at least one follow-up tumour evaluation.

The pharmacokinetic/biomarker population will be a subset of the safety and efficacy populations and consist of all patients who have sufficient NOX66 plasma data or biomarker plasma data for analysis. All such patients will be evaluated unless significant protocol deviations have impacted the data. Changes to the procedures, which may impact the quality of pharmacokinetic data, will be considered significant protocol deviations. Examples include sample processing errors that lead to inaccurate bio-analytical results and/or inaccurate dosing on the day of pharmacokinetic sampling.

3.2 Visit windows

The Screening visit must be at least 7 days prior to the first dose of NOX66.

All other visits should be within ± 1 day of the planned study visit. All visits will be analysed based on the planned visit, as opposed to when the visit actually occurred.

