### 10.1.2 Phase 1b (Combination) Arm

As each patient completes 1 Treatment Cycle of the Run-In Arm, they will be offered the combination treatment and may commence that combination treatment immediately providing

that there is no residual toxicity > Grade 1 or in the opinion of the Investigator has recovered from any Study-associated toxicity. Each patient will receive the same idronoxil dosage as they received in the Run-In Arm. A Treatment Cycle is 28-days.

Idronoxil treatment will be daily for 7 consecutive days, commencing on Day 1 and continuing until Day 7.

Carboplatin treatment will be administered intravenously on Day 2 of the Treatment Cycle, starting with a carboplatin dosage of AUC=4 for the initial 3 Treatment Cycles, before proceeding to an AUC=6 for up to 3 remaining Treatment Cycles.

The maximum dosage of carboplatin that may be administered per Treatment Cycle is 600 mg (AUC=4) and 900 mg (AUC=6).

Patients can receive up to 6 treatment cycles of combination therapy at the discretion of the Investigator provided that the patient is not experiencing DLT and the patient, in the opinion of the Investigator, is not experiencing disease progression.

DLT during the Combination Arm of the Study will be managed as a result of discussion between the Investigator, the Medical Monitor and the Sponsor and could involve withholding of idronoxil and/or carboplatin until the patient recovers, and/or a reduction in the dosage of idronoxil and/or carboplatin through a change to a lower idronoxil and/or carboplatin dosage.

If DLT recurs on re-introduction of treatment, the future of that patient is to be discussed with the Medical Monitor.

If a second patient develops a DLT within any treatment regimen, then dose escalation will cease and the prior dose level will be declared the MTD for the combination therapy.

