**Table 6. Schedule of Assessments -Phase Ib (Combination) Arm**

Study Day 	Commencing Treatment Cycle				Second and subsequent treatment cycles				End of Study 
	1 	2 	7 	15	1	2	7	15	
Physical Examination (PE)		X	X	X	X	X	X	X	X
12 Lead ECG 		X	X			X			X
ECOG Performance Status		X	X	X			X	X	X
Vital Signs 		X	X	X	X	X	X	X	X
Clinical laboratory tests									
Complete Blood Count (CBC)		X	X	X	X		X	X	X
Serum chemistry		X	X	X	X		X	X	X
Pregnancy test (if applicable)									X
Concomitant medication review		X	X	X	X	X	X	X	X
Tumour imaging 									
PK/Biomarker sampling 			X				X		
Adverse events/toxicity assessment		X	X	X	X	X	X	X	X
Dispense study drug	X				X				

 There is ± 1-day window allowable for each clinic visit.

 Day 1: Commence NOX66 treatment

 Day 2: Return study drug for in-clinic administration; Carboplatin treatment 1-hour post-NOX66 administration;

 Day 7: Return study drug for in-clinic administration and conclude NOX66 treatment

 ECG 1-hour post-NOX66 administration

 Vital signs: = weight, blood pressure, pulse, respiratory rate and body temperature.

 Tumor burden to be assessed by CT/MRI according to the Investigator's judgement at minimum every 12 weeks.

Confirm objective response in 4 weeks.

 See Section 10.4.6 - 10.4.7 for the timing of collection of blood and urine for PK and blood for biomarker analyses.

 +28 – 33 days after last dose of Carboplatin treatment

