**Table 9. Schedule of Assessments - Phase IIa Arm**

Study Day 	Commencing Treatment Cycle				Second and subsequent treatment cycles				End of Study 
	1 	2 	7 	15	1	2	7	15	
Physical Examination (PE)	X	X	X	X	X	X	X	X	X
12 Lead ECG 			X			X			X
ECOG Performance Status	X		X	X			X	X	X
Vital Signs 	X	X	X	X	X	X	X	X	X
Clinical laboratory tests									
Complete Blood Count (CBC)	X		X	X	X		X	X	X
Serum chemistry	X		X	X	X		X	X	X
Pregnancy test (if applicable)									X
Concomitant medication review	X	X	X	X	X	X	X	X	X
Tumour imaging 									
Biomarker sampling 			X				X		
Adverse events/toxicity assessment	X	X	X	X	X	X	X	X	X
Dispense study drug	X				X				

 There is ± 1-day window allowable for each clinic visit.

 Day 1: Commence NOX66 treatment

 Day 2: Carboplatin treatment 1-hour post-NOX66 administration

 Day 7: Conclude NOX66 treatment

 ECG 1-hour post-NOX66 administration

 Vital signs: = weight, blood pressure, pulse, respiratory rate and body temperature.

 Tumor burden to be assessed by CT/MRI according to the Investigator's judgement at minimum every 12 weeks. Confirm objective response in 4 weeks.

 See Section 10.4.7 for the timing of collection of blood for biomarker analyses.

 +28 – 33 days after last dose of Carboplatin treatment

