**Table 10. PK Blood Sampling Schedule for Phase Ia (Run-In) Arm**

Day	Sampling time in relation to NOX66 administration
1	t = 0 (pre-dose), then 0.5, 1, and 2 hr post-dose*
8	t = 0 (pre-dose), then 1 hr and 2 hr post-dose*
15	t = 24 hr post-dose

\*Post dosing sampling may be taken following administration of the first suppository for Cohort 2 patients.

24-hour urine will be collected on Days 1, 8 and 15, commencing from the time of NOX66 administration on those days and returned at following visit day.

**Phase Ib (Combination) Arm:** Blood samples to be collected from all patients on Day 7 of each Treatment Cycle at t = 1hour post-dosing. Post dosing sampling may be taken following administration of the first suppository for Cohort 2 patients.

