**Table 11. Biomarker Blood Sampling Schedule for Phase Ia (Run-In) Arm**

Day	Sampling time in relation to NOX66 administration
1	t = 0 (pre-dose), then 1 hr post-dose*
8	t = 1 hr post-dose*
15	t = 24 hr post-dose

\*Post dosing sampling may be taken following administration of the first suppository for Cohort 2 patients.

**Phase Ib:** sample collected from all patients on Day 7 of each cycle, 1hour post dose. Post dosing sampling may be taken following administration of the first suppository for Cohort 2 patients.

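### SAP 3.2 files PK and biomarker samples under the planned visit day within a ±1-day window, so values drawn at very different times since the last NOX66 dose can be pooled under one label

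*SAP*

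**What the plan says.** **Visit rule.** SAP 3.2 sets the window, "All other visits should be within ± 1 day of the planned study visit", with screening as the only visit treated separately. It then adds the analysis rule, "All visits will be analysed based on the planned visit, as opposed to when the visit actually occurred". The footnotes to Protocol Tables 6 and 9 give the same window for Phases Ib and IIa: "There is ± 1-day window allowable for each clinic visit". Table 5, for the run-in, prints no window, so for that phase the ±1 day comes from the SAP alone.

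**Run-in Day 15.** Tables 5, 10 and 11 call for blood 24 h post-dose on Day 15. Table 7 shows NOX66 on Days 1 to 14 and rest from Day 15.

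**Phase Ib Day 7.** For PK, Protocol 10.4.6 says: "Blood samples to be collected from all patients on Day 7 of each Treatment Cycle at t = 1hour post-dosing". For biomarkers, 10.4.7 has: "sample collected from all patients on Day 7 of each cycle, 1hour post dose". Section 10.1.2 ends dosing that day: "Idronoxil treatment will be daily for 7 consecutive days, commencing on Day 1 and continuing until Day 7". Table 8 shows rest from Day 8 to Day 28. Table 6, footnote 4, ties the last dose to the visit: "Day 7: Return study drug for in-clinic administration and conclude NOX66 treatment".

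**Phase IIa Day 7.** Table 9 ticks biomarker sampling. Its footnote says only "Day 7: Conclude NOX66 treatment", and 10.4.7, to which the table refers, gives no Phase IIa sampling time.

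**Analysis.** SAP 8.6 tabulates biomarkers by cycle, cycle day and cohort. SAP section 11 assigns the biomarker tables to the safety population, and the plasma concentration and PK coefficient tables to the PK population. SAP 3.1 allows PK data to be left out after significant deviations and gives wrong dosing on the sampling day as an example. Appendix B has the date and time of draw written on each tube.

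**The concern.** For vital signs or routine chemistry, a one-day shift filed under the planned day does little harm. A drug concentration, or a marker expected to follow it, is different, because the scheduled time is defined in hours from a dose. Where the sampling day is the last dosing day or the day after it, one extra day can turn an on-drug value into an off-drug one, and the planned-visit rule then removes the difference from the tables.

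Day 15 is the only 24 h blood sample in the run-in, and Day 7 is the only PK and biomarker blood sample in each combination cycle. No second sample in the same cycle would expose a mistimed value. The synopsis wants plasma and biomarker levels correlated with anti-cancer activity and toxicity, and the biomarker correlation is a secondary objective. With eight patients planned per cohort, mixing exposure states under one label would typically weaken any true relation.

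**Working it through.** The plan states no figure on this point, so there is nothing to reproduce. The check takes elapsed times from the schedule and then shows how sensitive a concentration is to them.

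**Inputs from the documents:** window ±1 day (SAP 3.2; Tables 6 and 9); last run-in dose on Day 14 (Table 7); last combination-cycle dose on Day 7 (10.1.2, Table 8); Cohort 1 once daily and Cohort 2 every 12 h (Table 2); eight patients per cohort.

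**Assumptions:** sampling at the usual clock time of the first daily dose (Day 15) or 1 h after it (Day 7). The half-life is not given, so 12, 6 and 3 h are used as a range.

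**Step 1: run-in Day 15 sample.** Hours since the Cohort 1 Day 14 dose = 24 × (visit day − 14).
- Day 15: 24 × 1 = 24 h, as scheduled.
- Day 16: 24 × 2 = 48 h.
- Day 14: 0 h, that is, around the time of the final dose itself.

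In Cohort 2 the evening dose on Day 14 is 12 h later, so Day 15 gives 24 − 12 = 12 h and Day 16 gives 48 − 12 = 36 h. All of these are summarised as Day 15.

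**Step 2: effect on the Day 15 concentration.** With log-linear decline, C(24 h)/C(48 h) = 2^(24/half-life).
- 12 h: 2^2 = 4
- 6 h: 2^4 = 16
- 3 h: 2^8 = 256

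If one of eight otherwise similar patients is late, the cohort mean falls by (1 − 1/ratio)/8. That is 9.4%, 11.7% and 12.5% for the three half-lives.

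**Step 3: Phase Ib Day 7 visit held on Day 8.** The documents leave two branches open.
- (a) The clinic dose moves with the visit: the sample is 1 h post-dose and the timing is right.
- (b) Dosing ended on Day 7: the sample is 24 + 1 = 25 h after the last dose in Cohort 1, and 25 − 12 = 13 h in Cohort 2.

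A visit on Day 6 is still on treatment, so 1 h post-dose remains possible.

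**Step 4: effect under branch (b).** With simple decline from 1 h, the fraction left is 2^(−24/half-life) in Cohort 1 and 2^(−12/half-life) in Cohort 2.

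| Assumed half-life | Cohort 1 | Cohort 2 |
|---|---|---|
| 12 h | 25% | 50% |
| 6 h | 6.25% | 25% |
| 3 h | 0.4% | 6.25% |

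A one-compartment model with an assumed absorption rate of 1 to 3 per hour gives somewhat smaller Cohort 1 falls: 2.8–3.8-fold, 9.8–15.2-fold and 138–240-fold for 12, 6 and 3 h.

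**Step 5: which tables are affected.** The SAP 3.1 exclusion may remove some PK values. A patient who takes no dose on Day 8 is following Table 8, however, so it is unclear that this counts as wrong dosing. The biomarker tables use the safety population, and this exclusion does not filter them.

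**The case against.** A reader might infer that every Day 7 sample taken on Day 8 is off drug and is tabulated as 1 h post-dose. The documents do not support that. Table 6, footnote 4, places the final Phase Ib dose at the clinic visit, and each box holds a spare suppository, so the dose may travel with the visit. SAP 3.2 also assigns a day, not an hour. Both points stand. What remains is that a Day 8 dose conflicts with 10.1.2 and Table 8, that the documents choose neither branch, and that values of both kinds can therefore sit under Day 7.

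A reader might also carry the 1 h time over to Phase IIa. Section 10.4.7 gives that time only for Phase Ib, so the Phase IIa gap is a missing sampling time and not a mislabelled one.

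On the run-in, Table 5 prints no window and SAP 3.2 words it as something visits should meet. In addition, a sentence on urine collection in 10.4.6 speaks of NOX66 being given on Day 15. Table 7 puts Day 15 in the rest period, and a 24 h post-dose blood time fits a last dose on Day 14. The SAP window still applies to that visit.

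Finally, a PK analyst might use actual times for the parameters as a matter of course. SAP 7.2 refers only to standard analysis, and SAP 3.2 contains no such exception. The analyses are descriptive, the Day 7 sample recurs each cycle, and plasma ratios say nothing direct about the size of a biomarker error. These points limit the impact but do not remove the rule.

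**Conclusion.** The concern holds as a defect in a stated rule, not merely as missing detail. SAP 3.2 applies planned-visit analysis to samples that are defined by hours since dose. The run-in Day 15 sample shows it most plainly, because no scheduled dose at the visit can correct the timing: about 48 h is summarised as the 24 h sample in Cohort 1. For Phase Ib Day 7 the conclusion is conditional. On-drug and off-drug values can be pooled, but the documents do not prescribe that outcome.

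The ratios of 4, 16 and 256 rest on assumed half-lives and log-linear decline and describe plasma concentration only. On Day 7, the twice-daily cohort is less affected than the once-daily one. How often visits run a day late is unknown. The exposure is greatest for the biomarker tables, which the PK exclusion does not reach. The change is worth making before the analysis, since it is cheap and the draw times are already recorded.

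**What to change.** 1. In SAP 3.2, exempt PK and biomarker samples from the planned-visit rule.
2. Derive actual hours since the last recorded NOX66 dose from the draw time on the tube and a recorded time of last dose. The CRF is not among the documents, so check whether it already holds that time and add a field if it does not.
3. State a tolerance around each nominal time. Keep a value in the nominal-time summary and in the correlations only if it falls within that tolerance, and list the others with their actual times. Apply this to the biomarker tables as well as to the PK population.
4. Have the sponsor reconcile three items: the ±1-day window (SAP 3.2; Tables 6 and 9), the Day 7 dose taken in clinic (Table 6, footnote 4), and the rest period from Day 8 (section 10.1.2, Table 8). Which reading applies is the sponsor's decision.
5. State the Phase IIa biomarker sampling time in Protocol 10.4.7.

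The cost is a paragraph of SAP text, a protocol clarification and possibly one CRF field. The downside is that a few samples may drop out of the nominal-time summaries, though they stay in the listings.

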3.3 General statistical methodology

Patients will be analysed by both study arm and dose cohort. Patients will be assigned sequentially to the two cohorts of 400 mg NOX66 (1 suppository per day) or 800 mg NOX66 (2 suppositories per day). Each cohort will be identified by '400 mg' or '800 mg'. The first 16 patients recruited to the study will be included in the study arm identified as 'Phase I' that will consist of a 21-day monotherapy phase and combination phase of up to 6 x 28-day cycles. Additional replaced patients will be included in the combination phase of up to 6 x 28-day cycles with the highest tolerated NOX66 dose cohort.

Descriptive statistics or continuous measures will include number of observations (n), mean, standard deviations (SD), minimum, median and maximum. For categorical measures, the descriptive statistics will include count and percent of the cohort.

There are four investigative sites in this study. There will be no analysis by study site.

The Medical Dictionary for Regulatory Affairs (MedDRA) will be used to code both medical history events and adverse events recorded during the study. The latest available version of MedDRA will be used to perform the coding at the end of the study. The World Health Organization (WHO) Drug Dictionary (DD) will be used to code concomitant medications taken prior to and during the study treatment period. The latest available version of WHO DD will be used to perform the coding at the end of the study.

As this is a dose escalation study, an 'Overall' column will be calculated for all tables.

All programming will be done in SAS version 9.4.

Missing data will remain missing with the exception that, for safety data, if there are corresponding unscheduled visits where data values exist, and those data are missing for the prior, scheduled, visit, then the values from the unscheduled visit will be imputed.

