### 7.1 Phase I Arm

In the **Phase Ia (Run-In) Arm**, patients will self-administer idronoxil rectally either once or twice (12-hourly) daily for 14 consecutive days for one (21-day) Treatment Cycle using one of 2 idronoxil dosages.

The main purpose of the Phase Ia Arm is to confirm the tolerability of idronoxil (in the NOX66 dosage formulation) when used as a monotherapy over an extended period of treatment (14 consecutive days).

The **Phase Ib (Combination) Arm** will commence immediately following the Phase Ia (Run-In) Arm and will comprise idronoxil being administered in combination with carboplatin. Patients will remain in the same two starting cohorts and remain on the same idronoxil dosage.

Within each 28-day combination treatment cycle, idronoxil treatment will commence on Day 1 and continue daily for 7 consecutive days; carboplatin will be administered intravenously on Day 2.

There will be two different dosages of carboplatin administered: AUC = 4 and AUC = 6. Patients will start with the lower dose and receive that for 3 Treatment Cycles. Providing there is no DLT, patients then will progress onto the higher dosage of carboplatin which they will receive for up to a further 3 Treatment Cycles.

The primary aim of this phase is to see if idronoxil can induce a meaningful clinical response (complete or partial remission by RECIST) in combination with carboplatin in cancers that have stopped responding to standard chemotherapy and generally would be considered unlikely to respond to further standard therapy. And then further, to see if this meaningful combination anti-cancer effect is possible with a dosage of carboplatin that would be regarded generally as being well tolerated but unlikely to deliver a significant anti-cancer effect.

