2.2 Study design

This is a Phase I, open-label, non-randomised, dose-escalation (two-step) study of the experimental drug, NOX66, in a suppository dosage formulation (NOX66) in patients with refractory solid tumours that have stopped responding to standard treatment options. The patients will have solid cancers selected from 5 phenotypes: prostate, breast, ovarian, lung, head and neck.

The study has two confirmed arms: a Phase Ia (Run-In) Arm where NOX66 is used alone and a Phase Ib (Combination) Arm where NOX66 is used in combination with carboplatin.

A Phase IIa arm is a potential third arm. This will only be triggered by clinical responses in the Phase Ib arm that are considered by the Investigators to be meaningful.

Sixteen (16) evaluable patients will be recruited and 8 patients allocated to each of two cohorts – Cohort 1 and Cohort 2. Cohort 1 will receive an NOX66 dosage of 400 mg daily; Cohort 2, 800 mg daily. Recruitment into Cohort 2 will not occur until at least 7/8 Cohort 1 patients have completed at least 1 Phase Ia Treatment Cycle without Dose-limiting Toxicity (DLT).

In the **Phase Ia (Run-In) Arm**, patients will self-administer NOX66 rectally either once or twice (12-hourly) daily for 14 consecutive days for one (21-day) Treatment Cycle.

The main purpose of the Phase Ia Arm is to confirm the tolerability of NOX66 formulation when used for 14 consecutive days in a 21-day monotherapy cycle..

The **Phase Ib (Combination) Arm** will commence immediately following the Phase Ia (Run-In) Arm and will comprise NOX66 being administered in combination with carboplatin. Patients will continue in the same cohorts and remain on the same NOX66 dosage.

Within each 28-day combination treatment cycle, NOX66 treatment will commence on Day 1 and continue daily for 7 consecutive days; carboplatin will be administered intravenously on Day 2.

There will be two different dosages of carboplatin administered: AUC = 4 (600 mg maximum) and AUC = 6 (900 mg maximum). Patients will start with the lower dose and receive that for 3 Treatment Cycles, then progress onto the higher dosage of carboplatin which they will receive for up to a further 3 Treatment Cycles.

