8.2 Adverse events

Adverse events will be coded by MedDRA SOC and Preferred Term, summarised and tabulated for the safety population in the monotherapy arm (phase 1a), in combination arm (phase 1b) with low dose (AUC4) carboplatin and with high dose (AUC6) carboplatin and overall treatment. For each preferred term the number and percent of subjects reporting each adverse event will be tabulated by cohort and 'Overall'. These include:

- Adverse event summary table
- Adverse events occurring prior to study commencement
- All adverse events occurring after study commencement
- Most common (>15 %) treatment-emergent adverse events in any cohort
- Treatment emergent adverse events that were possibly, likely or certainly related to the study medication
- Serious adverse events
- Severe adverse events
- Adverse events causing withdrawal
- All adverse events by maximum severity and relationship to study treatment, with subject identification.

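### Adverse events are split by carboplatin period, but the only stated denominator is the cohort, so the AUC 6 percentages are understated unless every patient reaches combination cycle 4

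*SAP*

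**What the plan says.** Four statements bear on the denominator.

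- SAP 8.2 tabulates adverse events for monotherapy and then "in combination arm (phase 1b) with low dose (AUC4) carboplatin and with high dose (AUC6) carboplatin and overall treatment". For each preferred term it asks for a count and a percentage of patients, by cohort and overall. It does not say what the percentage is a percentage of.
- SAP 3.3 supplies the general rule: "For categorical measures, the descriptive statistics will include count and percent of the cohort".
- SAP 3.1 fixes the population: "The safety population will consist of all patients who received at least one dose of NOX66. This population will be used in all safety summaries".
- SAP 2.2 gives the planned size: "Sixteen (16) evaluable patients will be recruited and 8 patients allocated to each of two cohorts".

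The periods follow one another within a patient. In Phase Ib, three cycles at AUC 4 come before up to three at AUC 6 (SAP 2.2; Protocol 7.1 and 10.1.2). Protocol 7.1 adds a condition: "Providing there is no DLT, patients then will progress onto the higher dosage of carboplatin". Protocol 10.1.2 lets combination cycles continue only while there is no DLT and, in the investigator's opinion, no progression.

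SAP 8.1 defines exposure as a span of dates and does not split it by carboplatin dose. SAP 8.3 tabulates serious adverse events in the same way as all adverse events, so it inherits the same denominator.

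**The concern.** A percentage in a treatment-period column is read as the risk for patients given that treatment. If the divisor is the cohort, patients who left before the period began stay in the denominator and can contribute nothing to the numerator. The earlier patients drop out, the safer the later period looks.

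This matters most at AUC 6, the last period and the higher carboplatin dose. Tolerability alone and with carboplatin is part of the first primary objective (Protocol 6.1). Protocol 13.1 says the study is meant to guide which dosage combination goes into later studies. A reader comparing the AUC 4 and AUC 6 columns would see a difference that mixes toxicity with attrition, and the error favours the higher dose.

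**Working it through.** The documents give no adverse event rate and no retention figure, so there is no planned number to reproduce. The check is arithmetic on the stated rule.

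**Inputs**
- N = 8 patients per cohort (SAP 2.2).
- m = patients in the cohort who receive AUC 6. Not stated; taken as 2 to 8 for illustration.
- x = patients with a given event during AUC 6, with x no larger than m.

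**Formula**
- Reported percentage = x/N.
- Percentage among those treated = x/m.
- Since x/N = (x/m) × (m/N), the reported figure is the treated-patient figure multiplied by m/N.

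**Two patients with an event at AUC 6, N = 8**

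| m | Reported, 2/8 | Among treated, 2/m | m/N |
|---|---|---|---|
| 8 | 25.0% | 25.0% | 1.000 |
| 7 | 25.0% | 28.6% | 0.875 |
| 6 | 25.0% | 33.3% | 0.750 |
| 5 | 25.0% | 40.0% | 0.625 |
| 4 | 25.0% | 50.0% | 0.500 |
| 3 | 25.0% | 66.7% | 0.375 |
| 2 | 25.0% | 100.0% | 0.250 |

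In terms of rates, a 40% rate among treated patients would be reported as 0.40 × 0.75 = 30%, 0.40 × 0.50 = 20% or 0.40 × 0.25 = 10% when 75%, 50% or 25% of the cohort reach AUC 6.

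**Is full retention plausible?** A patient who starts in the run-in reaches AUC 6 after 21 + 3 × 28 = 105 days, or 15 weeks. The eligibility criteria require a life expectancy of only 12 weeks (Protocol 8.2), and imaging is due at least every 12 weeks (Protocol 10.3.1), so progression will normally have been looked for by then. If 10%, 20% or 30% of patients were lost per cycle over the three AUC 4 cycles (assumed), the share reaching AUC 6 would be 0.9³ = 73%, 0.8³ = 51% or 0.7³ = 34%.

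**The AUC 4 column.** The same formula applies, with m now the patients who start combination treatment. If one patient in a cohort of 8 stops in the run-in (assumed), two AUC 4 events show as 25.0% instead of 2/7 = 28.6%. The effect is smaller than at AUC 6 because fewer patients have had time to leave.

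**Precision.** With m = 4, the exact (Clopper-Pearson) 95% interval is 6.8% to 93.2% for 2/4, against 3.2% to 65.1% for 2/8. The cohort denominator therefore also makes the AUC 6 figure look more precise than the data allow.

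**The case against.** The best reply is that SAP 3.3 states a generic rule and also says that patients are analysed by study arm as well as by cohort. On that view, the reference in SAP 8.2 to the safety population in each arm already limits the denominator to patients in that arm. The wording allows this for monotherapy against combination, although SAP 3.3 also uses the term study arm for Phase I as a whole. It does not rescue the AUC 6 column: AUC 4 and AUC 6 sit in the same combination arm, so patients who stop during AUC 4 would still be counted at AUC 6.

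A second reply is that little hangs on these percentages. Much of this stands. Counts accompany every percentage, SAP 4.1 reports cycles completed by phase and cohort, and a reader could partly rebuild m. The escalation and MTD rules use counts of patients with toxicity or DLT, and the Phase IIa combination is chosen by agreement (Protocol 10.1.3). A reader might infer that the denominator could steer a dose decision; the documents contain no decision rule that uses it.

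Three further inferences are tempting and not supported:

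- **That the threshold for common events would hide AUC 6 events.** SAP 8.2 words that table as "Most common (>15 %) treatment-emergent adverse events in any cohort", which is by cohort and not by period, and all events after study commencement are tabulated as well.
- **That replacement patients certainly dilute the monotherapy column.** They may start at Phase Ib cycle 1 (Protocol 8.5), but SAP 3.3 places them in the combination phase. Dilution is only a possibility, if the whole cohort were used as divisor despite that sentence.
- **That any DLT bars a patient from AUC 6.** Protocol 7.1 reads that way, but Protocol 10.1.2 also provides for withholding or reducing either drug and for re-introduction, and SAP 2.2 states no DLT condition. The point needs only that AUC 6 comes after three AUC 4 cycles.

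**Conclusion.** The point holds for the Phase Ib cohorts. Followed as written, the SAP divides AUC 6 events by a cohort that includes patients never given AUC 6. It is a stated rule that gives the wrong rate for part of a primary objective, so it is more than a missing detail.

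The AUC 6 percentage is too low by the factor m/N, and is correct only if every patient in the cohort reaches combination cycle 4. The size cannot be fixed from the documents because retention is not given; the m values above are illustrations, not predictions. N = 8 is the planned size, and replacements could make the 800 mg cohort larger.

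The point does not carry over automatically to Phase IIa. There, any one of the four dosage combinations may be chosen (Protocol 10.1.3), so AUC 6 need not follow three cycles at AUC 4.

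The SAP should be changed before the tables are produced. The understatement does not invalidate the safety data, which remain recoverable from counts and listings.

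**What to change.** In SAP 3.3 and 8.2:

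1. Set the denominator of each period column to the patients given one or more doses of that period's treatment: NOX66 alone in the run-in, NOX66 with carboplatin AUC 4, NOX66 with carboplatin AUC 6.
2. Print that n in each column heading, within cohort and overall.
3. Assign each event to a period by its onset date.
4. Keep the full cohort as the denominator of the overall-treatment column only.
5. Add a table note that the AUC 6 group is selected for having stayed on treatment through AUC 4, so its rates are not a like-for-like comparison with the AUC 4 column.

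Apply the same rule to the serious adverse event tables, which follow SAP 8.2. A line in SAP 8.1 giving cycles received per period would let readers check the n.

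The cost is SAP wording and table shells; no new data are needed. The downside is that AUC 6 percentages will be higher and rest on fewer patients, with intervals as wide as the 2/4 example. The new denominator corrects the arithmetic but does not remove the selection described in the note.
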